## **8.5. Pooling of Centers**

This study will be conducted at approximately 28 sites. All data will be combined for summaries and analyses.

## **8.6. Subgroups**

Selected analysis will be carried out further stratified by prior receipt of any biologics for psoriasis (bio-naïve vs non-bio-naïve, where bio-naïve is defined as not receiving any biologics for psoriasis previously and non-bio-naïve is defined otherwise), including primary efficacy analysis and selective secondary efficacy analysis for PASI scores (actual values, percent change from baseline at post-baseline visits, proportions of subjects achieving PASI-50, PASI-75, PASI-90 and PASI-100 at post-baseline visits).

This document is confidential.

## 9. Demographic, Other Baseline Characteristics and Medication

### 9.1. Subject Disposition and Withdrawals

This section describes subject disposition for both subject study status and the subject analysis populations.

The number of subjects screened, the number and percentage of subjects randomized and not randomized among all subjects screened, and the reasons for not being enrolled will be summarized. The above percentages will be calculated using the number of subjects screened as the denominator.

The number of subjects randomized and the number and percentage of subjects included in the safety analysis population, FAS, PPS, PK analysis set and CCI [REDACTED] will be summarized by treatment group and overall. Subjects withdrawing early and primary reason for withdrawal will be summarized. The above percentages will be calculated using the number of subjects enrolled as the denominator. The completion status and the reason for discontinuation will be listed.

A frequency table will be provided to summarize the number and percentages of randomized subjects excluded from the Safety Analysis Set, FAS, PPS, PK Set and CCI [REDACTED]. Additionally, reasons for exclusion will be summarized for each analysis set, where numbers and percentages for each CCI [REDACTED] category will be displayed. All percentages are based on the number of subjects randomized within each treatment group and overall. Listings of subjects excluded from the analysis populations, with the reasons for exclusions, will be provided.

### 9.2. Protocol Deviation

Major protocol deviations, as determined in the Blind Data Review Meeting (BDRM) prior to database lock, may result in the removal of a subject from the PPS.

The number and percentage of subjects with at least one major protocol deviation by type of deviation category will be presented by treatment group and overall. In addition, all protocol deviations (including both major and minor deviations) will be provided in a by-subject listing.

### 9.3. Demographic and Baseline Characteristics

Demographics and baseline characteristics will be summarized descriptively by treatment group and overall using Safety Analysis Set, FAS and PPS. The comparability of the treatment groups for each relevant characteristic will be assessed descriptively in table format; no statistical hypothesis tests will be performed on these characteristics.

For summaries (number and percentage) of categorical variables in demographics and baseline disease characteristics, a “missing” or “not applicable” level may be added (in addition to the levels specified below) to account for missing or not applicable data as appropriate.

#### 9.3.1. Demographics and Baseline Characteristics

Summary statistics will be provided by treatment group and overall for the following variables:

- Age (years)
- Sex (Male, Female)
- Child bearing potential for female subjects only (No, Yes)

This document is confidential.

- Race (White, Black or African American, Asian, Native Hawaiian or Pacific Islander, American Indian or Alaska Native)
- Ethnicity (Hispanic or Latino, Not Hispanic or Latino)
- Height (cm) at screening. Conversion to cm: Height (in inch) \* 2.64
- Weight (kg) at baseline. Conversion to kg: Weight (in lbs.) \* 0.4536
- BMI (kg/m^2)
- Previously Treated with Any Biologics for Psoriasis (Yes, No)
- Allergy or Toxicity of Previous Treatment (Yes, No)
- History of Substance Abuse (Yes, No)
- Smoking
  - Yes (Light, Moderate, Heavy, Other)
  - No (Past Smoker, Never Smoker)
- Alcohol Intake
  - Yes (Beer, Wine, Spirits, Other)
  - No

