## 4. Study Details/Design

### 4.1. Brief Description

This multi-center, randomized, double-blind, placebo-controlled, parallel group, Phase 2a study is designed to assess the efficacy and safety of ME3183 administered orally in subjects with moderate to severe plaque psoriasis. The study consists of a 4-week Screening Period (Day -28 to Day -1), a 16-week double-blind Treatment Period (Day 1 to Day 113), and a 4-week Follow-up Period (Day 114 to Day 141). The total duration of study participation for each subject is approximately 24 weeks.

[figure not shown]
Note: The study drug is administered from Day 1 to Day 112 in the Treatment Period and the end of Treatment Period assessments will be performed on Day 113.

The duration of the Follow-up Period is from Day 114 to Day 141 and the end of Follow-up Period assessments will be performed on Day 141.

A suitable number of subjects with moderate to severe plaque psoriasis will be screened to randomize approximately 125 subjects across approximately 30 study sites in the United States and Canada. Subjects will be centrally randomized (25 subjects per treatment group) in a 1:1:1:1:1 ratio to 1 of the following treatment groups to receive oral ME3183 or matching placebo for a duration of 16 weeks.

- Treatment Group 1: [REDACTED] mg ME3183 BID administered orally: [REDACTED] capsule of [REDACTED] mg ME3183 and [REDACTED] capsules of matching placebo in the morning and evening
- Treatment Group 2: [REDACTED] mg ME3183 QD administered orally: [REDACTED] capsules of [REDACTED] mg ME3183 and [REDACTED] capsule of matching placebo in the morning and [REDACTED] capsules of matching placebo in the evening
- Treatment Group 3: [REDACTED] mg ME3183 BID administered orally: [REDACTED] capsule of [REDACTED] mg ME3183 and [REDACTED] capsule of [REDACTED] mg ME3183 and [REDACTED] capsule of matching placebo in the morning and evening
- Treatment Group 4: [REDACTED] mg ME3183 QD administered orally: [REDACTED] capsules of [REDACTED] mg ME3183 in the morning and [REDACTED] capsules of matching placebo in the evening
- Treatment Group 5: Matching placebo BID administered orally: [REDACTED] capsules of matching placebo in the morning and evening

This document is confidential.

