### 8.2. Key Definitions

- Age will be collected in the eCRF and the derivation is defined as follows:  
Age = year of informed consent – year of birth
- BMI will be calculated using weight at baseline and height at screening using the formula below:  
$$\text{BMI (kg/m}^2\text{)} = \text{weight (kg)} / [\text{height (m)}]^2$$
- Baseline

Baseline is defined as the last non-missing assessment before the date/time of first dose of any study drug and includes assessments taken on Day 1, unless otherwise specified.

For PK analysis, the baseline values are those collected predose at all scheduled visits per Schedule of Assessments in [Table 1](#).

- Change from baseline

The change from baseline will be calculated for each post-baseline assessment as:

Change from baseline = Post-baseline value – baseline value

- Percent change from baseline

The percent change from baseline will be calculated for each post-baseline assessments as:

Percent change from baseline =

$$(\text{Post-baseline value} - \text{baseline value}) * 100 / \text{baseline value}$$

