## 18. Index of Tables

Table Number	Name	Analysis Set
14.1.1.1	Number of Subjects Enrolled and Study Termination	(Screened/Randomized Set)
14.1.2.1	Major Protocol Deviations	(Randomized Set)
14.1.2.2	Reasons for Exclusions from Analysis Sets	(Randomized Set)
14.1.3.1.1	Subject Demographic and Baseline Characteristics	(Randomized Set)
14.1.3.1.2	Subject Demographic and Baseline Characteristics	(Safety Analysis Set)
14.1.3.1.3	Subject Demographic and Baseline Characteristics	(Full Analysis Set)
14.1.3.1.4	Subject Demographic and Baseline Characteristics	(Per Protocol Set)
14.1.3.2.1	Baseline Disease Characteristics	(Randomized Set)
14.1.3.2.2	Baseline Disease Characteristics	(Safety Analysis Set)
14.1.3.2.3	Baseline Disease Characteristics	(Full Analysis Set)
14.1.3.2.4	Baseline Disease Characteristics	(Per Protocol Set)
14.1.3.3	Medical History	(Safety Analysis Set)
14.1.4.1.1	Prior Medications	(Safety Analysis Set)
14.1.4.1.2	Concomitant Medications	(Safety Analysis Set)
14.1.4.2.1	Prior Medical/Surgical Procedures	(Safety Analysis Set)
14.1.4.2.2	Concomitant Medical/Surgical Procedures	(Safety Analysis Set)
14.1.4.3	Prior Biologics or Systemic Treatment for Psoriasis	(Safety Analysis Set)
14.1.5	Extent of Exposure	(Safety Analysis Set)
14.1.6	Treatment Compliance	(Safety Analysis Set)
14.2.1.1.1.1	Proportion of Subjects Achieving PASI-75 at Week 16, Complete Case Analysis	(Full Analysis Set)
14.2.1.1.1.2	Proportion of Subjects Achieving PASI-75 at Week 16 Stratified by Receipt of Any Biologics for Psoriasis, Complete Case Analysis	(Full Analysis Set)
14.2.1.1.2.1	Proportion of Subjects Achieving PASI-75 at Week 16, LOCF	(Full Analysis Set)
14.2.1.1.2.2	Proportion of Subjects Achieving PASI-75 at Week 16 Stratified by Receipt of Any Biologics for Psoriasis, LOCF	(Full Analysis Set)
14.2.1.1.3.1	Proportion of Subjects Achieving PASI-75 at Week 16, NRI	(Full Analysis Set)
14.2.1.1.3.2	Proportion of Subjects Achieving PASI-75 at Week 16 Stratified by Receipt of Any Biologics for Psoriasis, NRI	(Full Analysis Set)
14.2.1.2.1.1	Proportion of Subjects Achieving PASI-75 at Week 16, Complete Case Analysis	(Per Protocol Set)
14.2.1.2.1.2	Proportion of Subjects Achieving PASI-75 at Week 16 Stratified by Receipt of Any Biologics for Psoriasis	(Per Protocol Set)
14.2.1.2.2.1	Proportion of Subjects Achieving PASI-75 at Week 16, LOCF	(Per Protocol Set)

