## 20. Index of Listings

Listing Number	Name	Analysis Set
16.2.1.1	Subject Disposition	(Screened Set)
16.2.1.2	Screen Failures	(Screened Set)
16.2.2	Subjects with Any Protocol Deviations	(Screened Set)
16.2.3	Subjects Excluded from Analysis Sets	(Screened Set)
16.2.4.1	Demographics and Baseline Characteristics	(Full Analysis Set)
16.2.4.2	Baseline Disease Characteristics	(Full Analysis Set)
16.2.4.3	Medical History	(Full Analysis Set)
16.2.4.4.1	Prior and Concomitant Medications	(Full Analysis Set)
16.2.4.4.2	Prior and Concomitant Medical/Surgical Procedures	(Full Analysis Set)
16.2.4.4.3	Prior Systemic Treatment for Psoriasis	(Full Analysis Set)
16.2.5.1	Study Drug Administration	(Full Analysis Set)
16.2.5.2	Study Drug Compliance	(Full Analysis Set)
16.2.6.1	Psoriasis Area and Severity Index (PSAI)	(Full Analysis Set)
16.2.6.2	Static Physician's Global Assessment (sPGA)	(Full Analysis Set)
16.2.6.3	Dermatology Life Quality Index (DLQI)	(Full Analysis Set)
16.2.6.4	Body Surface Area (BSA)	(Full Analysis Set)
16.2.6.5	Numerical Rating Scale (NRS)	(Full Analysis Set)
16.2.7.1	Treatment-Emergent Adverse Events	(Full Analysis Set)
16.2.7.2	Non-Treatment-Emergent Adverse Events	(Full Analysis Set)
16.2.8.1.1	Laboratory Reference Ranges	
16.2.8.1.2	Hematology and Coagulation	(Full Analysis Set)
16.2.8.1.3	Blood Chemistry	(Full Analysis Set)
16.2.8.1.4	Urinalysis (Dipstick)	(Full Analysis Set)
16.2.8.2.1	Vital Signs	(Full Analysis Set)
16.2.8.2.2	Electrocardiogram (ECG)	(Full Analysis Set)
16.2.8.2.3	Physical Examination	(Full Analysis Set)
16.2.8.2.4	Serology at Screening	(Full Analysis Set)
16.2.8.2.5	Serum Pregnancy Test and FSH at Screening	(Full Analysis Set)
16.2.8.2.6	Urine Pregnancy Test	(Full Analysis Set)
16.2.8.2.7	Individual Ctrough Concentrations	(Full Analysis Set)
CCI		

This document is confidential.

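### SAP 9.3.1 converts inches to centimetres with 2.64 instead of 2.54, so heights recorded in inches come out 3.9% too high and the BMI derived from them 7.4% too low

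*SAP*

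**What the plan says.** SAP section 9.3.1 lists the variables for the demographic summary and attaches unit conversions to two of them. For height at screening it gives "Conversion to cm: Height (in inch) \* 2.64". For weight at baseline, on the next line, it gives "Conversion to kg: Weight (in lbs.) \* 0.4536".

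BMI is in the same list. SAP section 8.2 states how it is derived: "BMI will be calculated using weight at baseline and height at screening using the formula below", and the formula is weight in kg over the square of height in metres. The 9.3.1 rule is the only inch conversion in either document.

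These variables appear under the title "Subject Demographic and Baseline Characteristics" in Tables 14.1.3.1.1 to 14.1.3.1.4, one each for the Randomized Set, Safety Analysis Set, Full Analysis Set and Per Protocol Set. Listing 16.2.4.1 is titled "Demographics and Baseline Characteristics". SAP section 9.3 explains the purpose of the tables: "The comparability of the treatment groups for each relevant characteristic will be assessed descriptively in table format", and adds that "no statistical hypothesis tests will be performed on these characteristics".

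**The concern.** The inch is defined as 2.54 cm, and no rounding of that gives 2.64. The line is a derivation rule in the finalized SAP (v3.0), and protocol section 15 lets the SAP prevail where the two documents differ. A programmer who follows the plan would therefore code 2.64, and a second programmer checking the code against the SAP would find agreement.

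The rule exists because entries in inches are expected. The trial runs at "approximately 30 study sites in the United States and Canada", where they are plausible.

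The accuracy of the reported height and BMI is at stake. This is the first study of the drug in the target patients (protocol section 5.4), and these tables describe who was treated. If some sites record inches and others centimetres, a single column would mix inflated and correct heights.

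**Working it through.** **Inputs**

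- Height factor in the plan: 2.64 cm per inch (SAP 9.3.1).
- Weight factor in the plan: 0.4536 kg per lb (SAP 9.3.1).
- BMI = weight (kg) / [height (m)]² (SAP 8.2).
- True unit values: 2.54 cm per inch and 0.45359237 kg per lb. These are unit definitions and are not stated in the documents.

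**1. Do the plan's factors reproduce?** The weight factor does: 0.4536 / 0.45359237 − 1 = +0.0017%, which is rounding. The height factor does not: 2.64 against 2.54. The nearest explanation is one wrong digit.

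**2. Error in height.** 2.64 / 2.54 = 1.03937, so a height recorded in inches is reported 3.94% too high.

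**3. Error in BMI.** Height enters squared in the denominator: (2.54 / 2.64)² = 0.92568, so BMI is reported 7.43% too low.

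**4. One subject, 70 inches and 220 lb.** Weight = 220 × 0.4536 = 99.79 kg.

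| | Plan's factor (2.64) | Correct factor (2.54) |
|---|---|---|
| Height | 70 × 2.64 = 184.8 cm | 70 × 2.54 = 177.8 cm |
| BMI | 99.79 / 1.848² = 29.2 | 99.79 / 1.778² = 31.6 |

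**5. Group means.** The documents do not give the share of heights recorded in inches, so I vary it. I assume true means of 170 cm and 30 kg/m² (not in the documents) and the same means whatever unit was recorded. The shift in mean height is share × 0.03937 × 170. The shift in mean BMI is share × (−0.07432) × 30.

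| Share in inches | Mean height | Mean BMI |
|---|---|---|
| 0% | 0 | 0 |
| 50% | +3.3 cm | −1.1 kg/m² |
| 100% | +6.7 cm | −2.2 kg/m² |

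With assumed true means from 165 to 175 cm and from 27 to 33 kg/m², the 100% row becomes +6.5 to +6.9 cm and −2.0 to −2.5 kg/m².

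**6. Between arms.** A false difference arises only if the share in inches differs between arms. For illustration, suppose two arms of 25 differ by 5 such subjects, a difference in share of 5/25 = 0.20. The false differences are 0.20 × 6.69 = 1.3 cm and 0.20 × 2.23 = 0.45 kg/m².

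**7. Reach.** I checked where height or BMI is used in the readable SAP text. Neither enters the primary CMH analysis (10.1), the MMRM, log-rank or Cox analyses (10.2), or the subgroups (8.6). The vital-sign summaries (13.3) use body weight but not height.

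**The case against.** The strongest case on the other side accepts the error and disputes its importance.

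- **No effect on results is shown.** The documents do not establish that any height was recorded in inches or that the printed constant was coded. SAP section 17 provides for checks of program logic and review of output, and a mean height several centimetres too high might be noticed there. This stands as a limit on the size of the effect. The written rule is still wrong, and a check of code against the SAP would confirm it.
- **Comparability of arms is barely touched.** Allocation is central and randomised, so the recording unit has no systematic link to arm, and the 5-in-25 imbalance is hypothetical. With an assumed height SD of 8 to 11 cm (not in the documents), the standard error of a difference between two arms of 25 is SD × √(2/25), or 2.3 to 3.1 cm. The illustrative 1.3 cm lies inside chance variation. The disease-characteristic tables and the other demographic variables, which also describe baseline balance, are unaffected. This stands too: the main harm is to the absolute values of height and BMI.
- **The content of Listing 16.2.4.1 is not visible.** Only its title is given, and the shells are in a separate document. Whether it prints converted height or BMI has to be checked.
- **A digit could have been misread from the PDF.** The neighbouring 0.4536 came through cleanly and nothing suggests corruption. The signed SAP would settle it.

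**Conclusion.** The concern holds. The height conversion in SAP 9.3.1 is wrong as written. For each height recorded in inches and converted by that rule, reported height is 3.9% too high and BMI 7.4% too low. These two percentages rest only on the definition of the inch and the SAP's own BMI formula. The shift in group means depends on the unknown share recorded in inches. Under the means assumed above it runs from nothing to about 6.7 cm and 2.2 kg/m².

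The consequence is descriptive. No efficacy or safety analysis in the readable text changes. The documents do not show that the screening BMI criterion (protocol section 8.1) or membership of the Per Protocol Set depends on this conversion. The correction should be made because the rule gives wrong numbers whenever it is applied and costs almost nothing to put right.

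**What to change.** In SAP section 9.3.1, replace 2.64 with 2.54. Search the programs that derive height and BMI for the same constant. If 2.64 was used, correct it and rerun Tables 14.1.3.1.1 to 14.1.3.1.4, and Listing 16.2.4.1 if its shell shows that it prints converted height or BMI.

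The cost is one digit in the SAP and a check of one constant. If the constant was used, add a rerun of four tables and at most one listing.

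If the outputs have already been produced, comparing a few reported heights with the recorded inches will show which factor was applied.

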#### 9.3.2. Baseline Clinical Characteristics

Baseline clinical characteristics will be summarized descriptively by treatment group and overall and will include the following:

- Age at initial diagnosis of psoriasis (years)
- Duration of plaque psoriasis (from date of initial diagnosis to the date of informed consent; year, presented with one decimal of accuracy)
- Type of psoriasis at initial diagnosis (Plaque, Guttate, Pustular, Inverse, Erythrodermic, Nail psoriasis, Psoriatic arthritis, Not known)
- Severity of psoriasis at initial diagnosis (Mild, Moderate, Severe, Unknown)
- Prior treatment for psoriasis (Yes, No)
- Any associated types of psoriasis other than plaque at screening (Yes, No)
- Other associated types of psoriasis at screening (Guttate, Pustular, Inverse, Erythrodermic, Nail psoriasis)

#### 9.4. Medical History

Medical history terms will be coded using the Medical Dictionary for Regulatory Activities (MedDRA) dictionary Version 24.1 or later. A frequency table (with number and percentage) of medical history will be presented by treatment group and overall in terms of system organ class (SOC) and preferred term (PT) for the Safety Analysis Set.

#### 9.5. Prior and Concomitant Medications and Procedures

Medications will be coded using the World Health Organization (WHO) Drug Dictionary Version September 2021 or later, and subject incidence will be tabulated by Anatomic Therapeutic Class (ATC) Level 2 and preferred term (PT) for the Safety Analysis Set. The systemic medication of psoriasis will be summarized and listed separately.

Prior procedures will be collected with medical history, coded using MedDRA Version 24.1 or later and summarized by SOC and PT for the Safety Analysis Set.

This document is confidential.

See [Section 8.3](#) for handling of partial dates for medications/procedures, in the case where it is not possible to define a medication/procedures as prior, concomitant, or post treatment.

- Prior medications/procedures are the medications/procedures which started and stopped prior to the first dose of study drug.
- Concomitant medications/procedures are medications/procedures which started prior to, on or after the first dose of study drug and before or on the date of last dose of study drug.
- Post medications/procedures are medications/procedures which started after the last dose of study drug.

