15.4 Safety Analyses

All safety analyses will be performed using the safety analysis set. All recorded AE and SAEs will be listed and tabulated by Medical Dictionary for Regulatory Activities (version 24.1 or higher) system organ class, preferred term, and treatment group over the 16-week Treatment Period and the 4-week Follow-up Period.

The incidence of TEAEs (events with onset dates on or after the first dose of the study drug or that was present prior to dosing and exacerbates after the first dose of study drug) will be included in incidence tables. Events with missing onset dates will be included as TEAEs. If a subject experiences more than 1 occurrence of the same AE, the occurrence with the greatest severity and the closest association with the study drug will be used in the summary tables. SAEs and AEs causing study discontinuation will be tabulated. All AEs will be listed by subject, along with information regarding onset, duration, relationship and severity to study drug, seriousness, action taken with study drug, treatment of event, and outcome.

Vital signs and safety laboratory results will be listed and summarized by treatment group over the 16-week Treatment Period and the 4-week Follow-up Period. Summaries will be provided using descriptive statistics, including mean values and mean change from Baseline values, as well as numbers of subjects with values outside limits of the normal range at each time point.

Any CS physical examination findings and safety laboratory results will be summarized. ECG readings will be evaluated by the investigator and abnormalities, if present, will be summarized and listed. The clinically noteworthy QT/QTc interval (> 450 , > 480 , or > 500 msec) or clinically noteworthy change from Baseline (> 30 or > 60 msec) will also be summarized using descriptive statistics.

Summary tables will be provided for concomitant medications initiated during the study period.

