### 8.3. Missing Data

For the purposes of assessing treatment emergence for AEs or classifying medications into prior/concomitant, the following algorithms will be used for partially missing dates. However, the assessment times (start date, stop date) without imputation will be presented in the listings.

For start dates of events:

This document is confidential.

- Only the year is reported:
  - If the participant did not receive any study drug (i.e., study intervention start date is missing), then start date will be set to 'January 1'
  - If the participant received the study drug (i.e., study intervention start date is not missing):
    - If the year of the start date is identical to that of the study intervention start date and the stop date contains a full date and earlier than the study intervention start date, then start date will be set to 'January 1', otherwise the start date will be set to the study intervention start date.
    - If the year of the start date is not identical to that of the study intervention start date, then the start date will be set to 'January 1'.
- Only the month and year are reported:
  - If the participant did not receive any study drug, then the start date will be set to the 1st day of the month.
  - If the participant received any study drug:
    - If the month and year are identical to the month and year of the study intervention start date, and the stop date contains a full date earlier than the study intervention start date, then the start date is set to the 1st day of the month, otherwise set start date to the study intervention start date.
    - If the month and year are not identical to the month and year of the study intervention start date, the start date will be set to the 1st day of the month.

For stop dates of events:

- Only the year is reported: if the last visit is in the reported year, the date of last visit will be used as the stop date; otherwise, '31 December' will be used as the stop date.
- Only the month and year are reported: if the last visit is in the reported month and year, the date of last visit will be used as the stop date; otherwise, the last day of the reported month and year will be used as the stop date.

If an AE has the start date completely missing, this AE will be considered as treatment-emergent, unless the stop date is before first dose of randomized study drug.

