If a medication has the stop date completely missing, this medication will be considered as ongoing and concomitant.

There is no imputation for missing values in the safety analysis. The imputation of efficacy data is described in [Section 10](#).

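### SAP 9.5 defines concomitant therapy by start date alone, so, applied literally, items stopped before the first dose are classed as both prior and concomitant

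*SAP*

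**What the plan says.** SAP section 9.5 gives three definitions.

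- The prior class: "Prior medications/procedures are the medications/procedures which started and stopped prior to the first dose of study drug".
- The concomitant class: items "which started prior to, on or after the first dose of study drug and before or on the date of last dose of study drug".
- The post class: "Post medications/procedures are medications/procedures which started after the last dose of study drug".

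SAP section 8.3 adds rules for incomplete dates. It opens: "For the purposes of assessing treatment emergence for AEs or classifying medications into prior/concomitant, the following algorithms will be used for partially missing dates". It later says: "If a medication has the stop date completely missing, this medication will be considered as ongoing and concomitant".

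The Index of Tables (SAP section 18) has separate outputs on the Safety Analysis Set: Table 14.1.4.1.1, "Prior Medications", and Table 14.1.4.1.2, "Concomitant Medications". Procedures are split in the same way (14.1.4.2.1 and 14.1.4.2.2).

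Protocol section 15.4 describes the summary differently: "Summary tables will be provided for concomitant medications initiated during the study period". Protocol section 15 lets the SAP prevail where the two differ, and SAP section 14 declares no changes from the protocol's analyses.

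**The concern.** The prior definition uses both the start and the stop date; the concomitant definition uses only the start date. Nothing in the SAP says that an item already classed as prior cannot also be concomitant, and no order of precedence is given. A programmer who follows the sentence exactly would put every pre-treatment item into the on-treatment table as well.

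Such items are to be expected here. The exclusion criteria require several treatments to have stopped before the first dose; topical psoriasis treatments, for example, must not have been used in the preceding 2 weeks. A topical stopped to meet that criterion would then be tabulated as though it had been used during the study. The same applies to any short course of an unrelated drug that ended before Day 1. What is at stake is the accuracy of the descriptive concomitant tables and agreement between production and validation programs.

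**Working it through.** The SAP gives no figure to reproduce, so the check is logical. Let F be the first dose date and L the last dose date, with F ≤ L.

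**Rules as written (SAP 9.5)**
- Prior: start < F and stop < F.
- Concomitant: (start < F, or start = F, or start > F) and start ≤ L. The bracket is always true, so this is start ≤ L.
- Post: start > L.

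If an item is prior, then start < F ≤ L, so start ≤ L and it is also concomitant. Prior is a subset of concomitant.

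**Example.** Take F = Day 1 and L = Day 112 (the dosing period in SAP 4.1), and a topical started on Day −60 and stopped on Day −15. Prior holds, since −60 < 1 and −15 < 1. Concomitant also holds, since −60 ≤ 112.

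**Enumeration.** The rules were applied to every integer start from Day −60 to Day 141, with every stop from the start to Day 141, plus ongoing. The range is arbitrary and includes Day 0 as an integer; the counts only test the logic.
- All patterns: 202 starts, giving 202 × 203 / 2 + 202 = 20,705.
- Stopped before F: starts −60 to 0, giving 61 × 62 / 2 = 1,891. All 1,891 are both prior and concomitant.
- Post only: starts 113 to 141, giving 29 × 30 / 2 + 29 = 464.
- Concomitant only: 20,705 − 1,891 − 464 = 18,350.

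**With a stop-date condition** (start ≤ L, and stop ≥ F or ongoing), the 1,891 become prior only. The 18,350 and the 464 do not change, and no pattern falls in two classes or in none.

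**Two edge cases need their own wording**
- *Stops on Day 1.* Protocol 9.2 places the first dose on the evening of Day 1. An item stopped that morning has stopped before the first dose by clock time, yet its stop date equals F. If prior is judged by time and concomitant by date, it falls in both. On the grid, 62 patterns stop on Day 1 (starts −60 to 1). The enumeration above compares dates throughout, so it places them in concomitant only.
- *Started after L, stop date missing.* This is post under SAP 9.5 but concomitant under SAP 8.3. On the grid there are 29 such patterns (starts 113 to 141).

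**What the rest of the SAP implies.** Section 8.3 treats prior and concomitant as a classification, and its start-date imputation asks whether the stop date precedes the first dose. Section 9.5 introduces the partial-date rules as serving to place an item in one of three classes. Under the literal reading, the missing-stop-date sentence adds nothing to the concomitant class when the start is on or before L, and it contradicts the post definition when the start is after L. It serves a purpose only if the stop date was meant to count.

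**The case against.** The strongest reply is that the intended rule can be inferred. Section 8.3, the three-way wording of section 9.5 and the separate tables all point to exclusive classes, with the reference to earlier starts meant for therapy that continues into treatment. A programmer may well supply the missing condition. That stands as a reason to call the double tabulation conditional. It does not remove the point, because the operative sentence says something else and no other text supplies the condition.

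A reader might go further and infer that washed-out methotrexate or biologics will appear as prohibited on-study use, and that judgement of PASI confounding will suffer because SAP 7.1 handles events other than withdrawal by treatment policy. The documents do not support that much:

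- Prior systemic psoriasis treatment has its own eCRF page (SAP 9.6) and its own table (14.1.4.3). Protocol 12.1 also sends all prior psoriasis treatments to the prior and concomitant medications page, so duplication is possible but not established.
- Use of prohibited medication has its own deviation category (SAP 6.8). Major deviations are tabulated and all deviations are listed by subject (SAP 9.2).
- Listing 16.2.4.4.1 covers these medications by subject, and SAP 8.3 has unimputed dates shown in listings, so the true timing can be recovered for the subjects listed.
- No section names the concomitant table as the basis for judging confounding.

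Prior procedures are collected with medical history (SAP 9.5), so the practical overlap for procedures may be small.

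**Conclusion.** The definition is wrong as written. Applied literally, every item that meets the prior definition also meets the concomitant one, and Tables 14.1.4.1.2 and 14.1.4.2.2 are inflated. The clearest cases are topicals stopped for washout and non-psoriasis drugs, since neither has a separate route.

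The 100% overlap (1,891 of 1,891) follows from the logic. It might be read as a share of records misreported, but the documents do not say how many items will have stopped before the first dose, so no such estimate is possible.

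The effect is confined to descriptive tables. The primary endpoint, its test and its estimand do not use the section 9.5 classes, and per protocol membership rests on deviations settled at the blind data review meeting. The conclusion assumes that the sentence is programmed as it stands and that no separate specification already corrects it. This is a minor point, worth correcting because the correction is simple and has no drawback.

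**What to change.** 1. In SAP 9.5, define concomitant as a start date on or before the last dose date, and either a stop date on or after the first dose date or ongoing.
2. Define prior as a stop date before the first dose date, and state that both comparisons use calendar dates, so that an item stopped on Day 1 falls in concomitant only. The post definition can stay.
3. In SAP 8.3, state that a completely missing stop date makes a medication concomitant only if it started on or before the last dose date; if it started later, it is post.
4. Reconcile with protocol 15.4. The corrected SAP class includes therapy begun before the study and continued into treatment, which the protocol's summary does not. Either align the two or record the difference in SAP section 14.

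The cost is a few sentences in the SAP and the matching lines of the programming specification. No new data are needed.
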